## K. Timeline

The timeline to enroll between 36-39 subjects in this prospective randomized clinical pilot study is summarized in Table 4. IRB submission and coordination will occur within the first few months. Enrollment at each center will start as soon as central or local IRB approval is granted and proper training has been completed. We expect an average enrollment of 3 subjects per center completing recruitment and follow-up in 18 and 36 months, respectively.

**Table 4. Timeline of PAPS Pilot study**

Trimester (months)	Year 1			Year 2			Year 3		
	1 st	2 nd	3 rd	4 th	5 th	6 th	7 th	8 th	9 th
IRB submission	XX								
Coordination centers	XXXX								
Patient enrollment	XX	XXXX	XXXX	XXXX	XX				
Data Collection	X	XXXX	XXXX	XXXX	XXXX	XXXX	XXXX	XXXX	XXXX
Data analysis							XXXX	XXXX	XXXX
R01 preparation									XXXX

## L. Enrollment

We will engage clinicians/consultants to identify all subjects with frequent PVCs and mild to severe CM, regardless of duration, symptoms and heart failure during the following visits: 1) primary care and cardiology clinics, 2) device clinic referral for ICD implantation; 3) non-invasive laboratory with documented LV dysfunction by transthoracic echocardiogram and a minimum of >10 PVC/hour on average on at least a 24-hour Holter; 4) HF clinic with systolic LV dysfunction with frequent PVCs; 5) hospital admission to cardiac telemetry due to HF symptoms and PVC frequency of  $\geq 10$  PVC / hour. However, it is likely that most subjects will be identified through Part II, where we will screen all ambulatory Holters for PVC  $\geq 10\%$  and LVEF  $\leq 45\%$ . Refer to document Enrollment for further details.

***Estimate the prevalence of CM (LVEF ≤ 45%) and frequent PVCs (≥ 10%) in the overall population receiving ambulatory ECG Holter monitors.***

To prove the feasibility of a large randomized clinical trial (PAPS study), we plan to better estimate the prevalence of patients with PVC burden ≥10% and associated CM (LVEF ≤ 45%) in all consecutive adult patients undergoing at least a 24-hr ambulatory ECG monitor (Holter).

**A. Study Population and eligibility**

All consecutive adult patients prospectively and retrospectively who have undergone or will undergo local ambulatory ECG Holters (at least 24 hr) will be scrutinized for the presence of PVC ≥10% and LVEF ≤ 45% by reviewing a recent LVEF assessment (echocardiogram, MUGA or cardiac MR within 6 months of Holter date). If no LVEF is available, LVEF assessment should be considered to rule out associated CM as this would be clinically indicated. The enrollment goal is 1,500 unique subjects per center in the first 2 years for a total of near 20,000. Waiver of consent and waiver of HIPAA is requested for this portion of the study.

Retrospective and prospective data collection of this Holter data will allow each center to identify patients with potential diagnosis of PVC-cardiomyopathy, which could potentially be candidates for treatment randomization (Part I) if inclusion/exclusion criteria is met. Sites will collect Holter data retrospectively starting with Holters placed in July 2018 and forward.

**B. Data Management / Collection**

We will request that all centers provide PVC burden and LV ejection fraction in all-comers that undergo placement of an ambulatory ECG Holter regardless of duration (at least 24 hours).

Only, if PVCs are >10% on Holter, will centers provide further data including:

- Ambulatory Holter: mean heart rate, number of different PVC morphologies, PVC coupling interval.
- Echocardiographic data: LV end-diastolic and end-systolic dimension, LA size, if available.
- Upload a 12-lead ECG with representative PVC if available.

Once information is collected and entered in REDCap, each subject will receive a unique case number.

**C. Data Interpretation**

By reviewing Holters and LVEF in all subjects undergoing Holters, we will be able to estimate the prevalence of CM (LVEF ≤ 45%) and frequent PVCs (PVC burden ≥10%) in this specific population. We will calculate the prevalence of PVC-CM by dividing the number of subjects with frequent PVCs and CM by the overall subjects receiving Holters. As noted in our preliminary data, we speculate that the prevalence of both CM and frequent PVCs is 0.6% in subjects undergoing Holters. If our hypothesis is proven correct, we could demonstrate the potential magnitude of this clinical entity and the feasibility of the large-scale multicenter PAPS study by having 3 subjects with a potential PVC-CM diagnosis per 500 Holters.

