### Risks to Human Subjects

#### **a. Human Subjects Involvement, Characteristics, and Design**

##### ***Involvement of human subjects in the work outlined in the Research Strategy section.***

Premature ventricular contractions (PVCs) are frequently found in cardiomyopathy (CM) and heart failure (HF). Recently, high PVC burden has been associated with a reversible left ventricular (LV) systolic dysfunction, so-called PVC-induced CM (PVC-CM). Animal models have proven the concept that frequent PVCs can induce CM, which is reversed after eliminating PVCs. A current clinical conundrum is to recognize when PVCs are responsible for the development of a CM or secondary to a CM. Furthermore, it is unclear why the majority of subjects with frequent PVCs have a benign course, whereas up to one third develop CM.

Radiofrequency ablation (RFA) is an accepted intervention to restore LV function in CM potentially induced by PVCs, based solely on limited small retrospective studies. RFA can have risks as any other invasive procedure. Antiarrhythmic drugs (AAD) therapy is an alternative therapy offered to eliminate PVCs if subjects or physicians feel appropriate; however, no randomized-prospective study exists to understand the clinical outcomes and benefit of RFA when compared to AAD therapy. Appropriate diagnosis and treatment of PVC-CM could impact HF morbidity, mortality and healthcare spending.

These clinical relevant questions cannot be addressed in animal models. Thus, we propose this prospective multicenter randomized trial of subjects with CM and high PVC burden with a likely diagnosis of PVC-CM. This pilot study intends to provide the basis to design and power a large clinical randomized trial to assess reversal of CM associated with frequent PVCs between RFA and AADs and compare clinical benefits (improvement in quality of life, NYHA class, heart failure symptoms and decrease in hospital admissions) between RFA and AADs in PVC-CM.

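### Part II's prevalence formula counts every subject with PVC burden ≥10% and no LVEF as a non-case, so any true cases among them lower the estimate

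*Combined protocol and SAP*

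**What the plan says.** Part II is to estimate the prevalence of LVEF ≤45% together with PVC burden ≥10% in about 20,000 people having ambulatory monitoring. Section C (Data Interpretation) gives the only estimator: "We will calculate the prevalence of PVC-CM by dividing the number of subjects with frequent PVCs and CM by the overall subjects receiving Holters". It also states the expected result, "we speculate that the prevalence of both CM and frequent PVCs is 0.6% in subjects undergoing Holters", and links it to feasibility of the large trial through "having 3 subjects with a potential PVC-CM diagnosis per 500 Holters".

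Section A (Study Population and eligibility) takes LVEF from an echocardiogram, MUGA scan or cardiac MR within 6 months of the Holter. Where there is none: "If no LVEF is available, LVEF assessment should be considered to rule out associated CM as this would be clinically indicated". Part of the cohort is historical: "Sites will collect Holter data retrospectively starting with Holters placed in July 2018 and forward". Section B (Data Management / Collection) asks for the data broadly: "We will request that all centers provide PVC burden and LV ejection fraction in all-comers".

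None of these sections says how a subject with PVC burden ≥10% and no qualifying LVEF enters the ratio. The statistical section of Part I (section I) does not cover Part II or missing LVEF.

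**The concern.** Case status needs two facts, and the second may be missing. A subject with PVC burden below 10% is a non-case whatever the LVEF, so a missing value there does no harm. A subject with PVC burden ≥10% and no LVEF has unknown status, and the formula treats that unknown as a non-case.

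The collection steps need not close the gap. LVEF is requested, and testing is to be considered, but neither is binding. For the older Holters a new test may fall outside the 6-month window, and section D of Part II expects that some subjects cannot be reached.

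This ratio is the only estimate stated for Aim 2. The related hypothesis is that the condition is under-recognized, and people with frequent PVCs who were never imaged are where unrecognized cases could sit. A binomial confidence interval would not reveal the shortfall.

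**Working it through.** **The plan's own figures.** 3/500 = 0.6%, as stated. Thirteen centres at 1,500 each give 19,500, near the stated 20,000. At N = 20,000, 0.6% is 120 cases, with an exact (Clopper-Pearson) 95% interval of 0.498% to 0.717%.

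**Assumed inputs, not in the documents.**
- *u*: share of PVC ≥10% subjects with no qualifying LVEF.
- *r*: cardiomyopathy risk in unimaged relative to imaged PVC ≥10% subjects.
- True prevalence *P* = 0.6%, taking the plan's speculated figure as the truth.

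**Formulas.** Let *a* be the share of Holter subjects with PVC ≥10% and *c* the cardiomyopathy risk in the imaged ones. Then P = a·c·[(1−u) + u·r], so:
- stated ratio = a·c·(1−u) = P(1−u)/[(1−u) + u·r];
- conditional (product) estimate = a·c = P/[(1−u) + u·r].

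Example, u = 20%, r = 0.5: the denominator is 0.8 + 0.1 = 0.9, the ratio 0.6% × 0.8/0.9 = 0.53%, and the product 0.6%/0.9 = 0.67%.

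| r | u | Stated ratio (95% CI at expected count) | Product estimate |
|---|---|---|---|
| 1 | 5% | 0.57% (0.470–0.684) | 0.60% |
| 1 | 10% | 0.54% (0.443–0.652) | 0.60% |
| 1 | 20% | 0.48% (0.389–0.586) | 0.60% |
| 1 | 30% | 0.42% (0.335–0.520) | 0.60% |
| 0.5 | 10% | 0.57% (0.469–0.683) | 0.63% |
| 0.5 | 20% | 0.53% (0.437–0.644) | 0.67% |
| 0.5 | 30% | 0.49% (0.402–0.601) | 0.71% |
| 0.25 | 10% | 0.58% (0.483–0.699) | 0.65% |
| 0.25 | 20% | 0.56% (0.466–0.679) | 0.71% |
| 0.25 | 30% | 0.54% (0.445–0.654) | 0.77% |

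The expected interval excludes 0.6% from u of about 18% (r = 1), 30% (r = 0.5) and 47% (r = 0.25). At N = 19,500 these values barely change.

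**Bounds at u = 20%, r = 1.** The bounds also need the size of the PVC ≥10% group, another assumption. In both cases 120 × 0.8 = 96 cases are identified.
- The human-subjects section says "it is unclear why the majority of subjects with frequent PVCs have a benign course, whereas up to one third develop CM". If one third have cardiomyopathy, the group is 120 × 3 = 360 subjects, and 72 are unimaged. Lower bound 96/20,000 = 0.48%; upper bound (96 + 72)/20,000 = 0.84%.
- If only 12% have cardiomyopathy (illustration only), the group is 120/0.12 = 1,000, and 200 are unimaged. Upper bound (96 + 200)/20,000 = 1.48%.

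**A repair that does not work.** Removing the unimaged PVC ≥10% subjects from the denominator changes almost nothing. With a 5% group and u = 30%, 0.42%/(1 − 0.05 × 0.30) = 0.43%.

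**The case against.** The documents give neither the missing share nor the relative risk, so the bias may be trivial. At u = 5% the ratio is still 0.57% with r = 1, and 0.585% with r = 0.5, well inside the sampling interval for 0.6%. The request for LVEF in all-comers, and the statement that testing is clinically indicated, both push u down. This stands: the size is not established.

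The thresholds at which the interval excludes 0.6% are a yardstick of this review. Part II plans no interval and no test against 0.6%, and that figure may itself be an identified-case ratio. Clustering by centre would also raise the thresholds, to about 25%, 40% and 57% under an assumed design effect of 2. This stands too, so the thresholds only put the bias on the scale of sampling error.

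The figure of up to one third concerns developing cardiomyopathy, not its share in a Holter cohort, and the 12% has no source. Both only illustrate how wide the bounds could be.

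For recruitment planning the identified-case yield is the relevant quantity, and a shortfall is conservative. That is a good reason to keep the ratio, but not to call it prevalence, which is what Aim 2 asks for.

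Finally, the product estimate is not always an improvement. If unimaged subjects are at higher risk, for instance known cardiomyopathy with an echocardiogram older than 6 months, both figures fall short: at r = 1.5 and u = 20%, 0.44% and 0.55%. The upper bound covers that case.

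**Conclusion.** The concern holds. Followed literally, the formula classes every PVC ≥10% subject without an LVEF as a non-case, and any true case among them lowers the estimate. The direction is arithmetic and needs no assumption. The size does: with a true prevalence of 0.6% and equal risk, the relative shortfall equals the unimaged share (10% missing gives 0.54%, 30% gives 0.42%), and it shrinks if unimaged subjects are at lower risk. With about 20,000 Holters, a moderate missing share can matter as much as sampling error. This should be fixed before analysis. It does not damage the data, and it is confined to the PVC ≥10% group.

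**What to change.** In Study Design Part II, section C, keep all Holter subjects in the denominator and specify in advance:

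1. The current ratio, labelled as identified-case yield and as the lower bound for prevalence.
2. The product estimate: proportion with PVC ≥10%, times the proportion with LVEF ≤45% among PVC ≥10% subjects who have a qualifying LVEF. State that it assumes similar risk in imaged and unimaged subjects.
3. An upper bound that counts every PVC ≥10% subject without a qualifying LVEF as a case.
4. The number of PVC ≥10% subjects without a qualifying LVEF, by centre and by retrospective or prospective Holter.

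For any r between 0 and 1, items 1 and 2 bracket the true value apart from sampling error. Item 2 overshoots when unimaged subjects are at lower risk, so it belongs beside item 1 and should not replace it.

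The cost is analysis wording and possibly a Holter-date field. Section B does not list one, although the 6-month window already needs it. No added subjects or tests are required. The price is a wider reported range: in the 12% illustration the upper bound is about three times the lower (1.48/0.48).

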Study / Objectives	Estimate the prevalence of cardiomyopathy (CM, LVEF $\leq$ 45%) and frequent premature ventricular contractions (PVCs $\geq$ 10%) in the overall population receiving ambulatory ECG Holter monitors.
Primary hypothesis	The prevalence of CM (LVEF $\leq$ 45%) and frequent PVCs ( $\geq$ 10% burden) is largely under recognized in subjects undergoing ambulatory ECG Holters.
Study Design and duration	Multicenter prospective and retrospective population-based database of all subjects undergoing ambulatory ECG monitor during 24-month period.
Eligible subjects	All-comers undergoing at least a 24-hr ambulatory ECG monitor for any clinical indication
Planned number of subjects	A total of 20,000 ambulatory ECG monitors – 1,500 subjects per center (to be completed within 24 months).
Planned number of participating sites/ countries	At least 12 centers in the United States and one in Canada

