### **Impact of proposed PAPS pilot study**

This study will not only generate data to demonstrate the need of a clinical trial, but also to better design our large-scale multicenter randomized clinical trial, the PAPS study.

This grant application with a multidisciplinary approach intends to:

- 1) *Identify the prevalence of subjects with potential PVC-CM ( $\geq 10\%$  PVC burden and LVEF  $\leq 45\%$ ) in the overall population receiving Holters in participating tertiary high-volume centers.*
- 2) *Identify demographics, rate and limitations of enrollment, rate of responders (defined as improvement of LVEF  $\geq 10\%$ ; rationale found in Section: Approach – Study Design: Aim 2) during observation period and active PVC suppression, and potential crossover between PVC suppression arms (RFA and AADs).*
- 3) *Understand the feasibility and better design and power a large multicenter trial (PAPS Study).*

Thus, the proposed pilot study will pave the way for a large-scale multicenter randomized PAPS study to identify the best treatment strategy for subjects with PVC-CM.

---

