**D. Ethical / Regulatory Affairs**

The study will be conducted according to Good Clinical Practice Guidelines, the Declaration of Helsinki and US 21 CFR. Due to inaccessibility to some subjects, a waiver of informed consent and a waiver of HIPAA will be requested as some subjects may not be accessible for consent.

There is a possibility that during the screening of ambulatory ECG Holters and echocardiograms, we may find subjects with possible undiagnosed PVC-CM. Ethically, we would then be obligated to notify the primary care provider and/or cardiologist of a potential undiagnosed PVC-CM leaving it up to them to pursue further referral/interventions.

---

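### Part II cannot test its under-recognition hypothesis: no named data item shows whether a case was already known, and the only planned estimate is an overall prevalence with no comparator

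*Combined protocol and SAP*

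**What the plan says.** The Protocol Synopsis (Part II, Primary hypothesis) states that the prevalence of CM with frequent PVCs "is largely under recognized in subjects undergoing ambulatory ECG Holters". Specific Aims repeats this as hypothesis 4. The section on potential benefits of the research likewise says that the affected subjects are probably under-recognized. The Part II objective, given in the Synopsis and as Aim 2, is narrower: to estimate prevalence.

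Study Design Part II, section B sets out the data. For everyone: "We will request that all centers provide PVC burden and LV ejection fraction in all-comers that undergo placement of an ambulatory ECG Holter". For a subset: "Only, if PVCs are >10% on Holter, will centers provide further data including" three groups of items. The first is "Ambulatory Holter: mean heart rate, number of different PVC morphologies, PVC coupling interval". The others are LV and left atrial dimensions and a 12-lead ECG, both where available.

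Section C gives the analysis: "We will calculate the prevalence of PVC-CM by dividing the number of subjects with frequent PVCs and CM by the overall subjects receiving Holters". It speculates a prevalence of 0.6%, or 3 subjects per 500 Holters.

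Section D foresees that "we may find subjects with possible undiagnosed PVC-CM" and accepts a duty to tell the treating provider. It makes this status neither a data field nor an outcome.

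**The concern.** A hypothesis about recognition needs one of two things. Either each case is classified as known or not known before the index Holter, or the estimated prevalence is set against a stated figure for how common the condition was believed to be. Part II has neither. Known and newly found cases enter the numerator alike, and no threshold or reference value is given.

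The setting makes the distinction matter. The prevalence is to be estimated "in the overall population receiving Holters in participating tertiary high-volume centers", where some Holters may have been ordered because frequent PVCs or CM were already known. The documents do not say how many.

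At stake is whether about 20,000 Holter records can answer the question that Part II poses. If the plan is followed exactly, any prevalence it returns leaves that question open.

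**Working it through.** **Inputs from the documents**
- Speculated prevalence: 0.6%, or 3 per 500 Holters (Part II, section C).
- Size: 1,500 subjects per center, near 20,000 in total (Part II, section A); at least 12 US centers and one in Canada (Synopsis).
- Share of cases already recognized: not given. Assumed here to be 20% to 80%.

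**The plan's own figures**
- 3 / 500 = 0.006 = 0.6%, which agrees.
- 13 × 1,500 = 19,500, consistent with near 20,000.

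**Expected cases and precision of the prevalence**
- 0.006 × 20,000 = 120 cases; 0.006 × 19,500 = 117; 0.006 × 1,500 = 9 per center.
- The exact (Clopper-Pearson) 95% limits are the 2.5% point of Beta(x, n − x + 1) and the 97.5% point of Beta(x + 1, n − x). For 120/20,000 they are 0.50% and 0.72%; for 117/19,500 they are the same after rounding.

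The prevalence aim is therefore met with useful precision.

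**What the estimate says about recognition**

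Let K be the known cases and U the unrecognized ones. The planned estimator is (K + U) / N, which depends only on the sum.

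| Share already known (assumed) | K | U | Planned estimate | Prevalence of unrecognized cases, U / 20,000 |
|---|---|---|---|---|
| 20% | 24 | 96 | 0.60% | 0.48% |
| 50% | 60 | 60 | 0.60% | 0.30% |
| 80% | 96 | 24 | 0.60% | 0.12% |

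The planned estimate does not move while the quantity of interest changes fourfold. The factor of four reflects the assumed range; that the estimate stays fixed does not depend on it.

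**Whether another part of the plan supplies the information**
- History, cardiomyopathy duration and treatment are collected in Part I (section G, Data collection) or in the PVC-CM registry (section A.1). Both cover consenting subsets, not the Part II population.
- The only published PVC-CM frequency quoted (Specific Aims; Significance) is an incidence of 2.6 per 100,000. It cannot be compared with a prevalence among Holter patients.

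**Whether there would be enough cases if status were recorded**

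Exact 95% CIs for the share not previously documented, among 120 cases:
- 12/120 (10%): 5.3% to 16.8%
- 36/120 (30%): 22.0% to 39.0%
- 60/120 (50%): 40.7% to 59.3%
- 84/120 (70%): 61.0% to 78.0%
- 108/120 (90%): 83.2% to 94.7%

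The number of cases is adequate. What is missing is the variable.

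**The case against.** The best defense is that the hypothesis concerns prevalence, not individual patients. The Project Summary, Introduction and Significance sections call PVC-CM underestimated, and on that reading a prevalence ratio is the natural estimator. This has force, and the wording is ambiguous. It does not rescue the test, because that reading needs a comparator and none is set. The Enrollment, Retention and Follow Up Plans section estimates at least 3 subjects with the diagnosis treated per center within 2 years, against about 9 expected per center from Part II. That figure is a floor, concerns treated patients, is not tied to the Holter population and is not used in the analysis.

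It is also true that the list of further data is worded as open, that Part II is a descriptive arm of a pilot, and that Aim 2 can be met. None of this adds a field or analysis that bears on recognition.

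Three stronger readings are tempting but not supported:
- *Counting known cases overstates how many patients the full trial could recruit.* Table 1 does not require a new diagnosis. Known but untreated cases remain eligible. Previous PVC ablation, current class I or III drugs and recent amiodarone exclude; being already known does not.
- *Section C takes 0.6% as proof of the hypothesis.* Its sentence is conditional and concerns magnitude and feasibility.
- *Sites must already classify every case in order to notify providers, so the answer only needs recording.* Section D covers notification of possible undiagnosed cases. It does not require a ruling on each case.

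**Conclusion.** The point holds as a mismatch between hypothesis and data. Prevalence can be estimated (0.6%, 95% CI about 0.50% to 0.72%, if the speculated value is right), but under-recognition cannot be tested on either reading of the term. With about 120 expected cases, the unrecognized number could lie anywhere from 24 to 96 under the assumed 20% to 80% range, and the planned result would be identical.

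The conclusion rests on the items named in Part II, section B being the data collected, and on the plan's own 0.6%. No Part I endpoint or safety matter is affected. It should be corrected because the remedy is small and otherwise the Part II hypothesis goes unanswered.

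**What to change.** **Preferred.** In Part II, section B, for each subject with PVC burden ≥10% and LVEF ≤45%, add three separate chart-review fields:
- (a) frequent PVCs with CM documented before the index Holter: yes, no or unknown;
- (b) Holter ordered for known PVCs or known CM: yes or no;
- (c) previous PVC ablation, current class I or III drug, or amiodarone current or within 2 months, as in the Table 1 exclusions.

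Trigger these fields by the case definition (≥10%), since section B now asks for further data only above 10%.

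In section C, define under-recognition as the share of cases not previously documented, with an exact 95% CI, and state how unknowns are handled. Report prevalence overall and with known cases excluded. Base any statement about recruitable patients on (c), not (a).

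**Cost.** A short chart review of about 9 cases per center (about 120 in all), a few REDCap fields and a few sentences of analysis text. The data set covered by the requested waivers may need updating. Some misclassification will remain: where an outside diagnosis is missing from the local chart, a known case will look new and inflate the unrecognized share. The unknown category and field (b) limit this but do not remove it.

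**Alternative without new data.** Restate the Part II hypothesis as a prevalence estimate with its expected precision, and drop the wording on recognition.
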